6.10.3.4 Exploratory Efficacy Endpoints

Analyses of exploratory efficacy endpoints will be described in a separate SAP.

6.11 Bioanalytical and Pharmacokinetic/Pharmacodynamic Methods

All details involving pharmacokinetic/pharmacodynamic (PK/PD) analyses will be documented in a separate SAP.

6.12 Health Outcomes/Quality-of-Life Analyses

Analysis of the health outcomes/quality-of-life measures are described in [Table JAIA.6.6](#) and Section 6.4. The descriptions and high-level derivations are provided in [Table JAIA.6.4](#). Additional psychometric analyses will be documented in a separate analysis plan.

6.13 Safety Analyses

The definition of baseline and post-baseline are described in Section 6.3.

Safety analyses will include data from first dose of the study treatment and patients will be analyzed according to the investigational product which they were randomized at Week 0 (Visit 2). Safety analyses will use the safety population defined in [Table JAIA.6.1](#).

Safety topics that will be addressed include the following: AEs including TEAEs and SAEs, clinical laboratory evaluations, vital signs and physical characteristics, Columbia Suicide Severity Rating Scale (C-SSRS), the Self-Harm Supplemental Form, Quick Inventory of Depressive Symptomatology Self Report (QIDS-SR16), and safety in special groups and circumstances, including adverse events of special interest and investigational product interruptions.

For tables that summarize events (such as AEs, categorical lab abnormalities, shift to maximum severity), post-last dose follow-up data will be included. Follow-up data is defined as all data occurring up to and including 30 days after last dose of treatment. In general, for laboratory analytes and vital signs, planned (scheduled visits) and unplanned (unscheduled visits) measures are used for categorical analyses and planned (scheduled visits) measures are used for continuous by-visit analyses including change from last baseline to last postbaseline.

The planned safety analyses are consistent with compound level safety standards that are based on multiple sources, including company standards, internal and external subject matter experts,

and cross-industry initiatives (e.g., white papers produced by a PhUSE Computational Science Working Group [a collaboration with FDA and PhUSE], published in the PhUSE Deliverables Catalog at <https://www.phuse.eu/white-papers>). Descriptions of the safety analyses are provided in this SAP, however, additional details (such as handling of unscheduled visits, missing data, etc.) are in compound level safety standards.

The following statistical methods will be used for safety unless otherwise noted:

- Fisher's exact test will be used for treatment comparisons of proportions, and odds ratios with corresponding 95% CIs, where specified.
- Treatment differences in mean change for continuous measurements will be assessed using an ANCOVA model fitting "baseline" as a covariate. Type 3 sums of squares will be used.

Two-sided p-values are often reported yet should not be over-interpreted. For safety analyses, they are used primarily as a flagging mechanism.

Exposure-adjusted incidence rates (EAIR) will be calculated by treatment group. Incidence rate difference and ratio along with 95% CI may be provided for SAEs and AESIs.

The EAIR evaluating the incidence of a first event per 100 patient-years at risk (PYR) will be provided. Exposure will be calculated based on the analysis period defined as the treatment period plus up to 30 days off-drug follow-up time. Exposure time for a patient with an event will be counted up to the time of the start of event. Exposure time for a patient without an event will be censored at the end of the analysis period.

6.13.1 *Extent of Exposure*

Duration of exposure (in days) will be calculated as follows:

- Duration of exposure to investigational product is date of last dose of study drug – date of first dose of study drug +1.

Last dose of study drug is calculated as last date on study drug. See the compound-level safety standards for more details including imputation of missing last date on study drug.

Duration of exposure to study drug will be summarized using descriptive statistics (n, mean, standard deviation [SD], minimum, first quartile, median, third quartile, maximum). Cumulative exposure and duration of exposure will be summarized in terms of frequency counts and percentages by category and treatment group.

Exposure ranges will generally be reported in weeks using the following as a general guide:

- ≥ 4 weeks, ≥ 16 weeks, ≥ 24 weeks, ≥ 52 weeks
- >0 to <4 weeks, ≥ 4 weeks to <16 weeks, ≥ 16 weeks to <24 weeks, ≥ 24 to <52 weeks, and ≥ 52 weeks

Total patient-years (PY) of exposure to study drug will be reported for each treatment group for overall duration of exposure. Overall exposure will be summarized in total PY which is calculated according to the following formula:

Total patient-years of exposures (PYE) = sum of duration of exposure in days (for all patients in treatment group) / 365.25

6.13.2 Adverse Events

Adverse events are recorded in the eCRFs. Each AE will be coded to SOC and PT using the MedDRA version 24.0. Severity of AEs is recorded as mild, moderate, or severe.

A treatment-emergent adverse event (TEAE) is defined as an event that either first occurred or worsened in severity after the first dose of study treatment during the analysis period. The analysis period is defined as the treatment period plus up to 30 days off-drug follow-up time. Refer to the compound-level safety standards for more details.

In general, baseline measurements are those taken prior to starting study medication. Measurements taken during the treatment period are those taken after starting study medication, unless otherwise noted. If study drug is temporarily interrupted and subsequently restarted during the treatment period, the measurements taken during the temporary interruption will be included in the analysis. Where applicable, the time elapsed during the temporary interruption will also be included in analyses.

For events that are gender-specific (as defined by the MedDRA), the denominator and computation of the percentage will include only patients from the given sex.

Planned summaries are specified below and are described more fully in compound level safety standards and in the AE-related PhUSE white paper (Analysis and Displays Associated with Adverse Events: Focus on Adverse Events in Phase 2-4 Clinical Trials and Integrated Summary Document [PhUSE 2017]), available at <https://www.phuse.eu/white-papers>. All analyses will be conducted on the Safety Population.

Table JAIA.6.7. Summary Tables Related to Adverse Events

Analysis
An overview table, with the number and percentage of patients in the safety set with death, a SAE, any TEAE, discontinuation from the study due to an AE, permanent discontinuation from study drug due to an AE, or a severe TEAE
The number and percentage of patients with TEAEs using MedDRA PT nested within SOC
The number and percentage of patients with TEAEs using MedDRA PT (without regard to SOC)
The number and percentage of patients with TEAEs by maximum severity using MedDRA PT
The number and percentage of patients who experienced a serious adverse event (including deaths) using MedDRA PT nested within SOC
A listing of SAEs, deaths, AEs led to permanent study drug discontinuation during the study and listing of all temporary study drug interruptions, including interruptions for reasons other than AEs (abnormal laboratory)
The number and percentage of patients who permanently discontinued from study drug due to an adverse event (including adverse events that led to death) using MedDRA PT nested within SOC
The number and percentage of patients who temporarily interrupted study drug due to an adverse event using MedDRA PT nested within SOC
A summary of the number and percentage of patients who temporarily interrupted study drug, to include the number of interruptions per patient, and the duration and cumulative duration of interruptions
Listing of COVID-19 AE based on SMQ=20000237 using the narrow term classification
Summary of COVID-19 TEAE using MedDRA PT based on SMQ=20000237 with the narrow term classification

Abbreviations: AE = adverse event; MedDRA = Medical Dictionary for Regulatory Activities; PT = preferred term; PY = patient-year; SAE = serious adverse event; SMQ = Standardized MedDRA Query; SOC = System Organ Class; TEAE = treatment emergent adverse event.

In general, the number and percentage of patients with events will be summarized by treatment group in 2 formats:

- by MedDRA PT nested within SOC with decreasing frequency in SOC, and events ordered within each SOC by decreasing frequency in the baricitinib 4-mg group;
- by MedDRA PT with events ordered by decreasing frequency in the baricitinib 4-mg group.

6.13.3 Deaths, Other Serious Adverse Events, and Other Notable Adverse Events

The planned table and listing for SAEs are included in the previous section. A listing of deaths, regardless of when they occurred during the study, will also be provided.

6.13.4 Clinical Laboratory Evaluations

The planned summaries for clinical laboratory evaluations are provided in [Table JAIA.6.8](#) and are described more fully in compound level safety standards and in the laboratory-related PhUSE white papers (PhUSE 2013; PhUSE 2015).

All laboratory tests will be presented using the International System (SI) and United States conventional (CN) units.

There is one special circumstance for laboratory values to be derived. The low-density lipoprotein (LDL)/high-density lipoprotein (HDL) ratio will be derived as the ratio of LDL cholesterol to HDL cholesterol. Similarly, the ratio of HDL to LDL will be derived. There are no central laboratory reference ranges for the LDL/HDL or HDL/LDL ratio.

For the categorical laboratory analyses (shift and treatment-emergent), the analysis period is defined as the treatment period plus up to 30 days off-drug follow-up time. The analysis period for the continuous by-visit laboratory analyses including change from baseline by visit and to last observation is defined as the treatment period excluding off-drug follow-up time.

Table JAIA.6.8. Summary Tables Related to Clinical Laboratory Evaluation

Analysis
Box plots for observed values by visit and change from baseline by visit and at last observation excluding the follow-up period.
Tables with the number and percentage of patients who shift from normal/high to low (i.e., treatment-emergent low) and percentages of patients who shift from normal/low to high (i.e., treatment-emergent high).
Listing of abnormal findings for laboratory analyte measurements, including qualitative measures.

6.13.5 Vital Signs and Other Findings

For the treatment-emergent categorical analyses, the analysis period is defined as the treatment period plus up to 30 days off-drug follow-up time. The analysis period for the continuous by-visit laboratory analyses including change from baseline by visit and to last observation is defined as the treatment period excluding off-drug follow-up time.

The planned summaries for vital signs (systolic blood pressure [BP], diastolic BP, pulse, weight, BMI, temperature) are provided in [Table JAIA.6.10](#), and are described more fully in compound-level safety standards and in the vitals-related PhUSE white papers (PhUSE 2013; PhUSE 2015).

Table JAIA.6.9. Parameter Definitions Related to Vital Signs

Parameter	Low	High
Systolic BP (mm Hg) (Supine or sitting – forearm at heart level)	≤ 90 and decrease from baseline ≥ 20	≥ 140 and increase from baseline ≥ 20
Diastolic BP (mm Hg) (Supine or sitting – forearm at heart level)	≤ 50 and decrease from baseline ≥ 10	≥ 90 and increase from baseline ≥ 10
Pulse (bpm) (Supine or sitting)	< 50 and decrease from baseline ≥ 15	> 100 and increase from baseline ≥ 15
Weight (kg) (Consistent clothing and timing in relationship to meals and voiding)	(Loss) decrease $\geq 7\%$	(Gain) increase $\geq 7\%$
Temperature	< 96 degrees F and decrease ≥ 2 degrees F	≥ 101 degrees F and increase ≥ 2 degrees F

Table JAIA.6.10. Summary Tables Related to Vital Signs

Analysis
Box plots for observed values by visit and change from baseline values by visit and at last observation excluding the follow-up period.
Tables with the number and percentage of patients who shift from normal/high to low (i.e., treatment-emergent low) and percentages of patients who shift from normal/low to high (i.e., treatment-emergent high). For weight, the number and percentage of patients are based on a percentage gain/loss that exceeds defined limits. The limits are based on literature defined in Table JAIA.6.9 and in the compound level safety standards.

6.13.6 Safety Topics of Interest

Safety topics of interest include adverse events of special interest, potential toxicities that all products should consider (e.g., hepatic-related events), potential findings based on drug class, or topics anticipated to be requested by a regulatory agency for any reason.

6.13.6.1 Abnormal Hepatic Tests

Hepatic labs include alanine aminotransferase (ALT) and aspartate transaminase (AST), total bilirubin (TBL) and serum alkaline phosphatase (ALP). When criteria are met for hepatic evaluations, investigators will complete a follow-up hepatic safety eCRF. The planned summaries are provided in [Table JAIA.6.11](#).

Table JAIA.6.11. Summary Tables Relate to Hepatic Safety

Analysis
ALT and AST: The number and percentage of patients with a measurement greater than or equal to 3 times (3X), 5 times (5X), and 10 times (10X) the lab ULN during the analysis period for all patients with a post-baseline value and for subsets based on various levels of baseline value.
TBL: The number and percentage of patients with a measurement greater than or equal to 2 times (2X) the lab ULN during the analysis period for all patients with a post-baseline value and for subsets based on various levels of baseline value.
ALP: The number and percentage of patients with a measurement greater than or equal to 1.5 times (1.5X) the lab ULN during the analysis period for all patients with a post-baseline value and for subsets based on various levels of baseline value.
Lab Evaluation of Drug-Induced Serious Hepatotoxicity (eDISH) plot maximum postbaseline ALT divided by ULN vs. maximum postbaseline total bilirubin divided by ULN.
Patient profiles including demographics, disposition, information collected on the hepatic-safety CRF (where applicable) and a display of study drug exposure, adverse events, medications, blood pressure, heart rate, and the liver-related measurements over time will be provided for patients with information collected on the hepatic-safety CRF and any additional patients meeting ALT or AST measurement greater than or equal to 5X ULN (on a single measurement), or ALP measurement greater than or equal to 2X ULN (on a single measurement).

Summary Tables Relate to Hepatic Safety**Analysis**

Treatment-Emergent Potential Hepatic Disorders Based on MedDRA SMQs: treatment-emergent potentially drug-related hepatic disorders are defined by using the MedDRA preferred terms contained in any of the following SMQs:

- Broad and narrow terms in the Liver related investigations, signs and symptoms SMQ (20000008)
- Broad and narrow terms in the Cholestasis and jaundice of hepatic origin SMQ (20000009)
- Broad and narrow terms in the Hepatitis noninfections SMQ (20000010)
- Broad and narrow terms in the Hepatic failure, fibrosis and cirrhosis, and other liver damage SMQ (20000013)
- Narrow terms in the liver-related coagulation and bleeding disturbances SMQ (20000015)

Abbreviations: ALP = alkaline phosphatase; ALT = alanine transaminase; AST = aspartate aminotransferase;

CRF = case report form; MedDRA = Medical Dictionary for Regulatory Activities; SMQ = Standardized MedDRA Query; TBL = total bilirubin; ULN = upper limit of normal.

6.13.6.2 Hematologic Changes

Hematologic changes will be assessed through analysis of hemoglobin, white blood cell (leukocyte) count, absolute neutrophil count, lymphocyte count, and platelet count. The planned summaries are provided in [Table JAIA.6.12](#).

Table JAIA.6.12. Summary Tables Related to Hematologic Changes

Analysis

Shift tables showing the number and percentage of patients based on baseline to maximum during the analysis period will be created, with baseline depicted by the most extreme CTCAE grade during the baseline period. With each shift table, a summary displaying the number and percentage of patients who decreased, increased, or stayed the same in CTCAE grade category will be presented.

The number and percentage of patients with treatment-emergent shifts at any time during the analysis period, based on any increase to CTCAE Grade 1 or above, Grade 2 or above, Grade 3 or above, Grade 4.

Listing of patients with treatment-emergent thrombocytosis.

Abbreviations: CTCAE = Common Terminology Criteria for Adverse Events.

Treatment-emergent thrombocytosis as a laboratory-based abnormality will be defined as an increase in platelet count from a maximum baseline value \leq 600 billion/L to any postbaseline value $>$ 600 billion/L (Lengfelder et al. 1998). Similar analysis will use a cut-off of 400 billion/L. Planned and unplanned measurements will be included.

6.13.6.3 Lipid Effects

Lipid effects will be assessed through analysis of elevated total cholesterol, elevated low-density lipoprotein cholesterol, decreased and increased high-density lipoprotein cholesterol, and elevated triglycerides. The planned summaries are provided in [Table JAIA.6.13](#).

Table JAIA.6.13. Summary Tables Related to Lipid Effects

Analysis
Shift tables showing the number and percentage of patients based on baseline to maximum during the analysis period will be created, with baseline depicted by the most extreme NCEP-based level during the baseline period. With each shift table, a summary displaying the number and percentage of patients who decreased, increased, or stayed the same in NCEP-based level will be presented.
The number and percentage of patients with treatment-emergent shifts at any time during the analysis period, based on increases to various levels of NCEP-based categories.
The number and percentage of patients with treatment-emergent potential hyperlipidemia using a predefined MedDRA list of PTs that is a subset of the narrow scope PTs in the MedDRA SMQ “Dyslipidemia” (code 200000026) (see compound-level safety standards).

Abbreviations: MedDRA = Medical Dictionary for Regulatory Activities; NCEP =National Cholesterol Education Program; PT = preferred term; SMQ = Standardized MedDRA Query.

6.13.6.4 Renal Function Effects

Effects on renal function will be assessed through analysis of elevated creatinine. The planned summaries are provided in [Table JAIA.6.14](#).

Table JAIA.6.14. Summary Tables Related to Effects on Renal Function

Analysis
Shift tables showing the number and percentage of patients based on baseline to maximum during the treatment period will be created, with baseline depicted by the most extreme CTCAE grade during the baseline period. With each shift table, a summary displaying the number and percentage of patients who decreased, increased, or stayed the same in CTCAE grade category will be presented.
The number and percentage of patients with treatment-emergent shifts at any time during the treatment period, based on any increase to CTCAE Grade 1 or above, Grade 2 or above, Grade 3 or above, Grade 4 and above.

Abbreviation: CTCAE = Common Terminology Criteria for Adverse Events.

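### Table JAIA.6.14 gives the CTCAE creatinine tables a different window from the one Sections 6.13 and 6.13.4 set for shift and treatment-emergent laboratory analyses

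*SAP*

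**What the plan says.** The safety chapter sets one window for tables of this kind. Section 6.13 states: "For tables that summarize events (such as AEs, categorical lab abnormalities, shift to maximum severity), post-last dose follow-up data will be included". It then gives the length: "Follow-up data is defined as all data occurring up to and including 30 days after last dose of treatment". Section 6.13.4 repeats the rule for laboratory data and names both kinds of display: "For the categorical laboratory analyses (shift and treatment-emergent), the analysis period is defined as the treatment period plus up to 30 days" of off-drug follow-up.

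Table JAIA.6.14 in Section 6.13.6.4 has two rows, both graded by CTCAE. The section covers elevated creatinine only. The first row reads: "Shift tables showing the number and percentage of patients based on baseline to maximum during the treatment period will be created". The second counts patients with "treatment-emergent shifts at any time during the treatment period, based on any increase to CTCAE Grade 1 or above". Neither row mentions follow-up, and the section gives no reason for a separate window. The matching haematology row, in Table JAIA.6.12, reads: "treatment-emergent shifts at any time during the analysis period, based on any increase to CTCAE Grade 1 or above".

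**The concern.** The SAP uses two terms for two windows. The analysis period for categorical laboratory tables is the treatment period with off-drug time added, so the treatment period alone must be the shorter of the two. Table JAIA.6.14 holds exactly the two display types that Section 6.13.4 names, yet it uses the shorter term in both rows.

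Two programmers could therefore follow the same SAP and produce different renal tables. On the literal reading, a creatinine grade increase first seen after the last dose is left out of the only CTCAE renal displays in the plan. Under Section 6.13.2, an adverse event starting on that same day could count as treatment-emergent, so the laboratory and adverse event displays for one episode would cover different time spans. Renal function matters in this trial: Section 5.1 describes patients with reduced screening eGFR who are randomized and receive an adjusted dose.

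**Working it through.** There is no figure in the SAP to reproduce. The check is a comparison of the window each section or table uses for categorical displays.

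| Place in the SAP | Display | Window term |
|---|---|---|
| 6.13 | Categorical laboratory abnormalities, shifts to maximum severity | Includes data to 30 days after last dose |
| 6.13.4 | Laboratory shift and treatment-emergent tables | Analysis period (treatment plus up to 30 days) |
| 6.13.6.1, Table JAIA.6.11 | ALT, AST, bilirubin, ALP thresholds | Analysis period |
| 6.13.6.2, Table JAIA.6.12 | Haematology shift and treatment-emergent | Analysis period |
| 6.13.6.3, Table JAIA.6.13 | Lipid shift and treatment-emergent | Analysis period |
| 6.13.6.4, Table JAIA.6.14 | Creatinine shift and treatment-emergent | Treatment period, both rows |
| 6.13.6.5, Table JAIA.6.15 | CPK shift and treatment-emergent | Analysis period |

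1. *Is the renal table an outlier?* Yes. The four sister laboratory tables agree with each other and with the general rule. The first two CPK rows match the two renal rows word for word apart from this one term.

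2. *Is there a stated exception?* No. Section 6.13.6.4 gives none. The clause in Section 6.13, "The following statistical methods will be used for safety unless otherwise noted", introduces Fisher's exact test and ANCOVA. It concerns methods and does not cover data windows.

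3. *Which window was intended?* The revision history says that Version 2 changed the adverse event and treatment-emergent laboratory analyses by defining follow-up data to 30 days after last dose. That entry is not itself in conflict with anything. It does suggest that the renal wording was carried over and not chosen.

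4. *How large is the difference in window?* As an illustration, take a patient treated for the full 52 weeks, with the treatment period ending at the last dose:
   - treatment period: 52 × 7 = 364 days
   - analysis period: 364 + 30 = 394 days at most
   - share dropped on the literal reading: 30 / 394 = 7.6% at most

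   The share would be larger for a patient with less time on drug, under the same assumption. This is a share of calendar time. It says nothing about how many grade increases fall in that time.

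5. *What remains visible elsewhere?* Table JAIA.6.8 covers laboratory analytes generally under the 30-day rule. It tabulates shifts from normal or low to high and lists abnormal findings, and nothing in it excludes creatinine.

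**The case against.** The best defence is that the general rule is explicit and governs. Section 6.13.4 names shift and treatment-emergent laboratory analyses without exception, and a programmer who follows it would keep the off-drug values. Sections 6.13 and 6.13.4 also refer to compound-level safety standards for further detail, which are not shown and might settle the window. This stands as a limit on the consequence: loss of data is one of two readings. It does not remove the conflict, because the table is the more specific instruction and says something else.

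A reader might infer that creatinine rises after stopping drug would go uncounted altogether. The SAP does not support that, because Table JAIA.6.8 could still show a shift to high over the longer window. Only the CTCAE-graded displays are at issue.

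A reader might also infer that every patient who stops early loses 30 days of creatinine data, including the follow-up visit. That is not established either:

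- Section 6.13.4 does not define the treatment period by itself.
- The one explicit gloss, in Appendix 1 for medication review, runs from randomization to completion or early termination and is not tied to the last dose. The as-collected set in Table JAIA.6.5 uses observations made after treatment discontinuation, so some patients may remain in the study off drug. On the Appendix 1 gloss their later values would fall inside the treatment period.
- The SAP does not show the laboratory schedule, so it does not confirm a creatinine draw at the follow-up visit.

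**Conclusion.** The inconsistency is real and should be corrected. Both rows of Table JAIA.6.14 conflict with the window that Sections 6.13 and 6.13.4 set for these display types, and with the four sister laboratory tables. On the literal reading, creatinine CTCAE grade increases first seen in the off-drug follow-up window are left out of both renal displays.

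The size is small. The windows differ by at most 30 days per patient, on the assumption that the treatment period ends at the last dose. The number of patients affected cannot be derived from the SAP. The issue is confined to one safety table and does not touch the primary or any multiplicity-controlled analysis. It is more than clerical, because the wording decides which values enter the table.

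**What to change.** Replace treatment period with analysis period in both rows of Table JAIA.6.14. This brings the renal table under the rule in Section 6.13.4 and in line with the hepatic, haematology, lipid and CPK tables. If the narrower window was deliberate, Section 6.13.6.4 should say so, give the reason, and state where the window ends. The cost is one term changed in two rows. No new data, test or display is needed.
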